4.4 Measure to minimize bias

Study participants eligible for treatment will be randomly assigned to one of the five treatment arms using a computer-generated stratified randomization code. The random allocation sequence will be generated by using an algorithm which minimizes deviations from the anticipated arm sizes stratified by 2 levels of baseline infection intensity (light: 1-999 EPG, and moderate plus heavy: ≥ 1000 EPG *T. trichiura* infections) which will be provided by the trial statistician not involved in enrolment, treatment and data collection. This way, all treatment arms will have a similar proportion of participants with light infection intensity. The number of light *versus* moderate/heavy infections however are not expected to be equal in each arm, depending on the distribution of infection intensity in the recruited cohort. Allocation concealment will be warranted by masking the randomization sequence from the team member conducting the recruitment. Due to the complexity of the treatment scheme, blinding will not be feasible in order to avoid an unnecessary administration of a large amount of placebo pills. Masking of the outcome assessor is warranted since the laboratory technicians determining the egg counts for the efficacy assessment will have no knowledge of the participants' assignment to treatment arms.

4.5 Study duration and duration of subject participation

The trial will last 6 months, and screening for the baseline is scheduled to start 3 months prior to treatment. Follow-up screenings will take place between 14-21 days, 5-6 weeks and 3 months post-treatment and will last approximately three weeks respectively. Thus, the maximum time for subject participation will be 6 months. Schedules of visits are summarized below.

4.6 Schedule of visits

Table 1. Schedule of visits of during study.

	Screening Before day 0	Baseline/Treatment/Safety			Until day 7	Follow up		
		0h	3h	24h		14-21 days	5-6 weeks	3 months
Informed consent	X							
Diagnosis (stool examination)	X					X	X	X
Medical history		X						
Clinical examination		X						X
Pregnancy testing		X						
Hemoglobin measurement		X						
PK (micsosampling)	X		X	X	X			
Capturing AEs			X	X		X	X	X
Capturing SAE			X	X		X	X	X

5. Selection of the trial subjects

5.1 Recruitment

The study will be carried out in adolescents aged 12-19 years attending secondary schools on Pemba Island, Tanzania. Schools in areas with moderate to high *T. trichiura* infection intensities will be selected and identified based on experience from earlier studies and/or knowledge of the local collaborating teams. The trial will be implemented as a school-based study in order to simplify recruitment of adolescents. Caregivers of potential participants and adolescents aged ≥ 18 years will be invited to participate in an information session. The research team will explain the purpose and procedures of the study, as well as potential benefits and risks of participation. Attendees will be encouraged to ask questions which will be discussed in an open setting.

Caregivers interested in having their child/children of 12-17 years of age participate in the study or adolescents aged 18-19 years willing to participate will be invited to complete the process of informed consent by signing the informed consent form (ICF). In addition, written assent will be obtained from underage participants. Participants having a signed ICF will be assessed for eligibility during screening procedures.

5.2 Inclusion criteria

1. Aged between 12 and 19 years.
2. Written informed consent signed by either parents/caregivers for underage adolescents (aged 12-17 years) or by the participant him/herself (18-19 years of age); and written assent by underage participant.
3. Agree to comply with study procedures, including provision of two stool samples at the beginning (baseline) and on three follow-up assessments (14-21 days, 5-6 weeks and 3 months after treatment).
4. Willing to be examined by a study physician prior to treatment.
5. At least two slides of the quadruple Kato-Katz thick smears positive for *T. trichiura* and infection intensities of at least 48 EPG.

5.3 Exclusion criteria

1. No written informed consent by individual or caregiver and/or no written assent by minors
2. Presence or signs of major systemic illnesses, e.g. body temperature $\geq 38^{\circ}\text{C}$, severe anemia (below 80g/l Hb according to WHO [32]) upon initial clinical assessment.
3. History of acute or severe chronic disease.
4. Recent use of anthelmintic drug (within past 4 weeks).
5. Attending other clinical trials during the study.
6. Pregnancy, lactating, and/or planning to become pregnant within the next 6 months.
7. Known allergy to study medications (*i.e.* albendazole, ivermectin or moxidectin).
8. Taking medication with known interaction on study drugs.

5.4 Criteria for discontinuation of trial

A subject can be discontinued from the study for the following reasons:

1. Withdraws from the study (this can happen anytime as participation is voluntary and there are no further obligations once a participant withdraws).
2. At the discretion of the Principal Investigator (PI) or co-PI, if the participant is not compliant to the requirements of the protocol.

Discontinued subjects will not be replaced. If, for any reason, a subject is discontinued from the study before the end of treatment evaluations, the AE assessment will still be conducted. Data obtained prior to the withdrawal will be included in the analysis to ensure the validity of the trial. Data of withdrawn participants are fully anonymized once analysis is complete.

5.5 Treatment of subjects

After randomization, all eligible adolescents will be treated with the respective single or combination treatment regimen according to their assigned treatment arm at day 0. Albendazole will be the product of Glaxo Smith Kline (Zentel®) and a single tablet of 400 mg will be administered. Moxidectin tablets will be obtained from Medicines Development for Global Health (MDGH), Australia, and four tablets of 2 mg will be administered. Ivermectin tablets (3 mg) will be obtained from Merck (Stromectol®), and to administer a dose of 200 μ g/kg, the body weight of each participant will be recorded to calculate and administer the correct dose of ivermectin.

Since the study drugs are known to have an increased absorption in humans after a high-fat meal was consumed, participants will receive a local high-fat breakfast prior to treatment [16, 33, 34]. The tablets will be handed out from the drug container according to the randomization list. Each person will receive either:

- (i) A single tablet of albendazole plus four tablets of moxidectin
- (ii) A single tablet of albendazole plus the appropriate number of ivermectin tablets with regard to their body weight category
- (iii) A single tablet of albendazole
- (iv) The appropriate number of ivermectin tablets with regard to their weight category
- (v) Four tablets of moxidectin

All drugs will be administered in the presence of the PI and/ co-PI, and ingestion confirmed. This will be recorded with the time and date of dosing. Subjects will be asked not to take any drugs other than those prescribed by the study medical team. After ingestion of the medication, the subjects will be observed for 3 hours to ensure retention of the drug. Vomiting within 1-hour post-dosing will require re-dosing. The subjects will not be allowed more than one repeated dose. No re-administration will be needed for subjects vomiting after one hour. The PI or the co-PIs are responsible for drug accountability at the study site. Maintaining drug accountability includes careful and systematic study drug storage, handling, dispensing, and documentation of administration. Prior to administration, drugs will be stored at room temperature and protected from light and exposure to moisture in a secure area with limited access at the study site. The tablets must not be frozen or stored at temperatures above 30°C. Temperature monitors must be used for shipment and storage.

Treatment and capillary blood sampling (finger pricking) for the population PK and PK/PD assessment for a maximum of 60 study participants (maximum of 15 participants in the combination treatment arms and 10 participants in the monotherapy treatment arms) will be done in a quiet location at the school. Infrastructure as required for the study needs will be installed as necessary at the specific treatment days.

To avoid interference of potential on-going control programs against helminthiases with the infection status of the trial participants, communication with local stakeholders will be established to ascertain that trial participants will not undergo MDA treatment. Missed-out rounds of planned MDA against STH in the participating schools will be substituted with a free single-dose treatment (i.e., ivermectin 200 µg/kg/ albendazole 400 mg) against STH infection at the study endpoint (after the day 90 follow-up assessment) offered by the study team. At each follow-up time point, participants will be asked whether they had taken anthelmintic treatment.

5.6 Concomitant therapy

All medications taken one month before and during the study period until the last stool examination at the day 90 follow-up assessment must be recorded with indication, dose regimen, date and time of administration.

Medication(s)/treatment(s) permitted during the trial:

- Analgesics and antipyretics are allowed to be given to the subjects in case of fever, antiemetics to prevent nausea and vomiting and/or antibiotics to prevent or treat bacterial superinfection.

Medication(s)/treatment(s) NOT permitted during the trial:

- No other active drugs against helminths are permitted during the trial. Participants receiving active anthelmintic concomitant medication during the trial will not be discontinued, however a case-specific assessment will be done at the point of data-analysis.

6. Safety assessments

6.1 Adverse event definitions

The term “adverse event” is defined as follows:

Any untoward medical occurrence in a patient or clinical investigation subject administered a pharmaceutical product and which does not necessarily have to have a causal relationship with this treatment

An AE could therefore include any of the following events which develop or increase in severity during the course of the study after administration of the study product at treatment on day 0:

- a. Any unfavorable and unintended signs, symptoms or disease temporally associated with the use of a medicinal product, whether or not considered related to the condition under study and the study product
- b. Any abnormality detected during physical examination.

The medical conditions present at the initial trial visit that do not worsen in severity or frequency during the trial will not be defined as adverse events but considered as baseline medical conditions. For the purpose of this trial, disease progression and relapse will be considered as treatment failure, not as an Adverse Event.

The observation time for adverse events starts when the treatment is initiated until the end of the study. These data will be recorded on the appropriate CRF sections, regardless of whether they are thought to be associated with the study or the drug under investigation. Associated with the use of the drug means that there is a reasonable possibility that the event may have been caused by the drug (see also relatedness definitions below).

6.1.1 Severity grading

Adverse signs or symptoms will be graded by the physician or nurse of the trial as mild, moderate, severe or life threatening according to the following definitions:

Grade	Definition
1	Mild : the subject is aware of the event or symptom, but the event or symptom is easily tolerated.
2	Moderate : the subject experiences sufficient discomfort to interfere with or reduce his or her usual level of activity.
3	Severe : significant impairment of functioning: the subject is unable to carry out his or her usual activities.
4	Life threatening or disabling
5	Death related to adverse events

6.1.2 Relatedness

Relatedness will be assessed as defined below based on the temporal relationship between the adverse event and the treatment, known side effects of treatment, medical history, concomitant medication, course of the underlying disease and trial procedures.

Possibly related: an adverse event which can medically (pharmacologically/clinically) be attributed to the study treatment.

Unrelated: an adverse even which is not reasonably related to the study treatment. A reasonable alternative explanation must be available.

An adverse event that is determined to be related to the administration of a study product is referred to as an “adverse drug reaction.”

6.1.3 Expectedness

Expected adverse drug reaction: Any adverse event possibly related to the co-administration of ivermectin/ albendazole or moxidectin/ albendazole reported in the literature or on the drug package leaflets and listed in the consent form.

Unexpected adverse drug reaction: Any adverse event possibly related to the study product administration, the nature, frequency, specificity or severity of which is unanticipated and not consistent with the available risk information described for these drugs.

6.1.4 Serious adverse events

According to the ICH “Clinical Safety Data Management: Definitions and standards for expedited Reporting E2A” [35], a serious adverse event includes any event (experience) or reaction in any untoward medical occurrence that at any dose:

1. results in death;
2. is life threatening, meaning, the subject was, in the view of the Investigator, at immediate risk of death from the reaction as it occurred, *i.e.* it does not include a reaction that, had it occurred in a more serious form, might have caused death;
3. results in persistent or significant disability/incapacity, *i.e.* the event causes a substantial disruption of a person’s ability to conduct normal life functions;
4. requires in patient hospitalization or prolongation of existing hospitalization;
5. creates a congenital anomaly or birth defect (not relevant for this study);
6. is an important medical event, based upon appropriate medical judgment, that may jeopardize the patient or subject or may require medical or surgical intervention to prevent one of the other outcomes defining serious.

A “severe” adverse event does not necessarily meet the criteria for a “serious” adverse event. Serious adverse events are reported from treatment until the end of the study.

Serious adverse events that are still ongoing at the end of the study period will be followed up to determine the final outcome.

The causality of any serious adverse event that occurs after the study period and its possible relatedness to the study treatment or study participation will also be assessed by investigators as described in section 6.1.2.

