In this trial, we test for non-inferiority of both currently approved and available drug combinations (i.e. moxidectin/ albendazole against ivermectin/ albendazole) and for superiority of the combination therapy compared to the respective monotherapies. Furthermore, potential extended effects through a prolonged efficacy assessment scheme in adolescents in Pemba (Tanzania) are examined. Follow-up will be conducted at approx. 14-21 days, 5-6 weeks and 3 months post-treatment to assess co-benefits on worm burden reduction from the relatively long half-life of moxidectin ($T_{1/2}$: 491-832 hours) [11, 12] compared to ivermectin ($T_{1/2}$: 16-32 hours; increasing with age) [13]. Given the comparatively long half-life of moxidectin, the standard follow-up period of 14-21 days recommended by WHO might not be sufficient to reveal the full potential of the drug. Therefore, two more follow-up time points will give the opportunity to investigate potential extended effects on infection status and intensity. Results from this trial will inform decisions on how anthelminthic combination therapy could be introduced into existing MDA programs and, therefore, provide a valuable adjunct tool for interrupting STH transmission.

The pharmacokinetic/-dynamic (PK/PD) characterization of a drug is essential to understand the response of the human body to a drug and vice versa, especially in populations that physiologically differ from healthy adults. Physiological characteristic like mal- or undernutrition or intestinal worms, such as *T. trichiura*, can potentially affect the PK of a drug.[14, 15]. For moxidectin, clinical pharmacokinetics have so far exclusively been assessed in a limited number of healthy adults [16, 17]. A trial currently being conducted by our group will characterize PK and evaluate PK/PD parameters of moxidectin in adults infected with *Strongyloides stercoralis*. Our study will be the first one to provide information on the PK, PK/PD on all three drugs in this population and thus guide optimal drug dosing in *T. trichuris*-infected adolescence in Pemba. Additionally, we aim to provide novel information on the possible interplay of moxidectin and ivermectin with albendazole when co-administered. For this it is necessary to take not only samples in the combination arm but also in the monotherapy arms.

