4.3.3 Clinical examination

A clinical examination of the study participants assessing general health, anthropometric parameters including height and weight as well as tympanic temperature using an ear thermometer will precede the treatment. Each participant will be asked to provide a finger-prick blood sample for hemoglobin (Hb) levels, which will be detected using a HemoCue analyzer (Hb 301 system, Angelholm, Sweden). To avoid accidental treatment of pregnant girls/women all female participants will be asked to provide a urine sample to be subjected to a pregnancy RDT at baseline and at the end of the study 3 months after treatment. Girls/women will be individually counselled that they should not become pregnant during the entire study period. All trial participants will further be asked about existing clinical symptoms before drug administration.

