6.3 Reporting of serious adverse events

Any study-related unanticipated problem posing risk of harm to subjects or others (including all unexpected adverse drug reactions), and any type of serious adverse event (SAE) will be immediately (within a maximum of 24 hours after becoming aware of the event) notified to the study sponsor-investigator and co-PIs:

[name]. [name] (Sponsor-investigator)

Swiss Tropical and Public Health Institute

[name]

[contact]

[contact]

E-mail: [contact]

[name] (Co-PI)
Public Health Laboratory Ivo de Carneri
[name]
[contact]
[contact]
[contact]
Email: [contact]

Within the following 48 hours, the local co-investigator must provide to study sponsor-investigator further information on the serious adverse event or the unanticipated problem in the form of a written narrative. This should include a copy of a completed SAE form, and any other diagnostic information that will assist the understanding of the event. In exceptional circumstances, a serious adverse event may be reported by telephone. In these cases, a written report must be sent immediately thereafter by fax or e-mail. Names, addresses and telephone for serious adverse event reporting will be included in the trial-specific SAE form. Relevant pages from the CRF may be provided in parallel (e.g., medical history, concomitant medications).

All pregnancies must be reported to the Sponsor-Investigator promptly after becoming aware of the pregnancy. Treatment will not be administered at follow-up time points in the event of pregnancy. A study physician recruited from a local health facility/ hospital will serve as medical contact. The treating physician will follow up on the study participant until the pregnancy is resolved. The outcome of the pregnancy must be reported to the Sponsor-Investigator.

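### Section 6.1.4 sets aside the birth-defect criterion for an SAE although section 6.3 follows pregnancies to outcome, so a birth defect after exposure could miss the timed reports in section 6.4

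*Combined protocol and SAP*

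**What the plan says.** All references are to the combined protocol and SAP.

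- **Section 6.1.4** adopts the ICH E2A definition of a serious adverse event and lists six criteria. The fifth reads "creates a congenital anomaly or birth defect (not relevant for this study". The section limits SAE reporting to the time from treatment to the end of the study. It adds that the causality of an SAE arising after the study period will also be assessed.
- **Section 5.2** sets the age range ("Aged between 12 and 19 years") with no restriction by sex.
- **Section 5.3** excludes "Pregnancy, lactating, and/or planning to become pregnant within the next 6 months".
- **Section 4.3.3** says "all female participants will be asked to provide a urine sample to be subjected to a pregnancy RDT at baseline", and plans a second test at 3 months. It adds: "Girls/women will be individually counselled that they should not become pregnant during the entire study period".
- **Section 6.3** provides for pregnancies that occur anyway: "All pregnancies must be reported to the Sponsor-Investigator promptly after becoming aware of the pregnancy". The treating physician follows the participant until the pregnancy resolves. Then: "The outcome of the pregnancy must be reported to the Sponsor-Investigator".
- **Section 6.1.5** defines a SUSAR as an unexpected adverse drug reaction that is also an SAE.
- **Section 6.4** sets deadlines for reports to authorities and to the Swiss and Zanzibar ethics committees. Fatal or life-threatening cases are due within 24 hours, with a complete report within 7 further days. Other SAEs and SUSARs are due within 14 days.

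**The concern.** A protocol that follows every pregnancy to its outcome has accepted that exposed pregnancies may happen. It cannot consistently call the main adverse outcome of such a pregnancy irrelevant. The label matters because later safety rules take the SAE definition as their starting point: SUSAR status and the section 6.4 deadlines both depend on it. An investigator who follows section 6.1.4 literally would not class a birth defect as serious under the criterion written for it.

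At stake is whether authorities and both ethics committees hear of such a case on a fixed timetable. Section 11.2 establishes no data and safety monitoring board, so these reports are a principal outside check on safety.

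**Working it through.** The plan states no figure on this point, so there is none to reproduce. The check traces one hypothetical case, a birth defect in a child conceived around or after dosing, through the sections.

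**Step 1. Can the case arise?** Yes. Females are enrolled (5.2, 4.3.3). The exclusion in 5.3 covers those pregnant, lactating or planning pregnancy; it does not cover an unplanned pregnancy after dosing. Section 4.3.3 relies on testing and counselling, and sections 5.2 and 5.3 list no contraception requirement. Section 6.3 itself expects that pregnancies may occur.

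**Step 2. Does the sponsor-investigator learn of it?** Yes, through the pregnancy clause of 6.3. That clause asks for prompt reporting of the pregnancy. It sets no time limit for reporting the outcome and does not link an abnormal outcome to the SAE route.

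**Step 3. Is it an SAE?** Not under criterion 5, which is set aside. It could be one under criteria 1 to 4 or 6, but that takes a judgment. The adverse event definition in 6.1 concerns a person given the product, and criterion 6 concerns mainly harm to the patient or subject. A newborn is neither treated nor enrolled, so the fit is uncertain.

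**Step 4. Is it a SUSAR?** Only if step 3 gives an SAE, because 6.1.5 requires both an unexpected reaction and SAE status.

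**Step 5. Do the 6.4 deadlines apply?** They are written for SAEs and SUSARs. If steps 3 and 4 do not give that status, no dated report is required by the plan's own text.

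**Step 6. Does the event fall in the SAE reporting window?** Inputs:
- Last follow-up at 3 months, about day 90 (sections 4.5 and 5.6). Section 4.5 lets each follow-up round last about three weeks, which takes the end to about day 90 + 21 = 111.
- Conception on day 0 to day 90 after treatment (assumption).
- Gestation of 37 to 42 weeks from the last menstrual period, with conception two weeks after that date (assumption; the documents give no figure).

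Day of birth = day of conception + 7 × (gestation in weeks − 2).

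| Gestation | Conception on day 0 | Conception on day 90 |
|---|---|---|
| 37 weeks | 7 × 35 = day 245 | 245 + 90 = day 335 |
| 42 weeks | 7 × 40 = day 280 | 280 + 90 = day 370 |

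A term birth would fall at about day 245 to 370, after the end of the study in every case. For that period 6.1.4 offers only a causality assessment of SAEs, with no reporting deadline, and under criterion 5 the event is not an SAE in any case.

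**The case against.** The strongest reply is that the plan has other ways to catch such a case.

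- The 24-hour notification in 6.3 is not limited to SAEs. It also covers study-related unanticipated problems that put subjects or other people at risk, and every unexpected adverse drug reaction. Section 6.2 likewise lists unexpected reactions separately from SAEs.
- The remaining seriousness criteria stay open.
- Section 6.4 begins with a general duty to send safety notifications as the law requires and to give the same information to both ethics committees.
- Section 6.1.4 looks beyond the study period for causality, and the pregnancy follow-up in 6.3 has no cut-off at study end.
- The qualifier may simply reflect the exclusion of pregnant participants.

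Much of this stands. A reader might infer that a birth defect would escape expedited reporting altogether, or that it could never trigger the 24-hour notice. The documents do not support either reading: the outcome reaches the sponsor-investigator, and a case judged study-related and unanticipated has a 24-hour route.

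A reader might also take moxidectin's long half-life, or the number of participants given it, as a measure of the risk. Neither is one. Residual drug is not fetal risk, on which the documents give no figure, and the arm sizes count both sexes.

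The reply does not remove the contradiction. The unanticipated-problem route needs a prior judgment that the event is related or unexpected, and it ends with the sponsor-investigator and co-PIs. The general legal duty in 6.4 carries no stated deadline. The exclusions lower the chance of an exposed pregnancy without ruling it out. An investigator told that birth defects are not relevant is also steered away from using a general clause in their place.

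**Conclusion.** The point holds in a limited form. Section 6.1.4 is inconsistent with the pregnancy clause of 6.3. A birth defect after exposure is not automatically an SAE or SUSAR, so it could miss the timed reports in 6.4. Whether it did would depend on case-by-case judgment under another seriousness criterion or the unanticipated-problem clause. No reporting deadline is stated for events found after the last visit, and on the gestation assumption above that is when any term birth would occur.

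The size in events is small but cannot be calculated: the plan gives neither the number of females nor an expected number of pregnancies, and the exclusion, testing and counselling should keep pregnancies few. The contradiction itself rests on the text alone; only the timing of birth needs an assumption. The primary endpoint, power, sample size and efficacy analysis are unaffected. The change is worth making because a rare event of this kind is serious and the correction costs very little.

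**What to change.** 1. In section 6.1.4, delete the qualifier in brackets after criterion 5.
2. Reconcile 6.1.4, 6.3 and 6.4 by stating that a congenital anomaly or birth defect in any pregnancy reported under 6.3 is classified as an SAE and reported on the existing 6.3 and 6.4 timelines.
3. State that this applies equally when the event is found after the last study visit, so that the end-of-study limit on SAE reporting in 6.1.4 does not exclude it.

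The cost is wording only, through the amendment procedure in section 9.1. Pregnancy outcomes are already collected, so no new visit, test or data item is needed.
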